2.4.4.4 Analyses of tertiary efficacy endpoints and other endpoints

The analyses of tertiary efficacy endpoints and other endpoints will be presented with unadjusted p-values and considered exploratory. As with the primary effectiveness analysis, the tertiary effectiveness analyses and analyses of other endpoints will be performed on the mITT population as well.

For the analyses of the change from baseline in WOMAC A1, 7-day average WOMAC A1, WOMAC A, PTGA and COGA at Week 4, 8, 12, 16, 20, and the change from baseline in WOMAC B, C and total and quality of life at Week 4, 8, 12, 16, 20, 26, the same repeated-measures ANCOVA model as described in the primary analysis will be used. The changes from baseline to each visit for each parameter will be calculated. Means and adjust means of each treatment group will be provided, as well as adjusted mean and associated two-sided 95% CI of the difference between treatment groups.

For the change from baseline in the amount and days of permitted pain rescue medication at each post-baseline visit, the Wilcoxon Mann Whitney test will be performed.

2.4.5 Analyses of safety data

The summary of safety results will be presented by treatment groups.

General common rules

All safety analyses will be performed on the safety population as defined in [Section 2.3.2](#), unless otherwise specified, using the following common rules:

- Safety data in patients who do not belong to the safety population (eg, exposed but not randomized) will be listed separately
- The baseline value is defined generally as the last available value before randomization.
- The potentially clinically significant abnormality (PCSA) values are defined as abnormal values considered medically important by the Sponsor according to predefined criteria/thresholds based on literature review and defined by the Sponsor for clinical laboratory tests and vital signs.
- PCSA criteria will determine which patients had at least 1 PCSA during the treatment-emergent adverse event period, taking into account all evaluations performed during the

treatment-emergent adverse event period, including nonscheduled or repeated evaluations. The number of all such patients will be the numerator for the on-treatment PCSA percentage

- The treatment-emergent PCSA denominator by group for a given parameter will be based on the number of patients assessed for that given parameter in the treatment-emergent adverse event period by treatment group on the safety population.
- For quantitative safety parameters based on reading measurements, descriptive statistics will be used to summarize results and change from baseline values by visit and treatment group.
- The analysis of the safety variables will be essentially descriptive and no systematic testing is planned. Relative risks versus placebo and their 95% confidence intervals may be provided, if relevant
- selected safety analyses will be summarized by age, gender subgroups, and any pertinent subgroups as appropriate

2.4.5.1 Analyses of adverse events

Generalities

The primary focus of adverse event reporting will be on treatment-emergent adverse events. Pre-treatment adverse events will be described separately.

If an adverse event date/time of onset (occurrence, worsening, or becoming serious) is incomplete, an imputation algorithm will be used to classify the adverse event as pretreatment or treatment-emergent. The algorithm for imputing date/time of onset will be conservative and will classify an adverse event as treatment emergent unless there is definitive information to determine it is pre-treatment. Details on classification of adverse events with missing or partial onset dates are provided in [Section 2.5.3](#).

Adverse event incidence tables will present by SOC and PT, sorted in alphabetical order for each treatment group, the number (n) and percentage (%) of patients experiencing an adverse event. Multiple occurrences of the same event in the same patient will be counted only once in the tables within a treatment phase. The denominator for computation of percentages is the safety population within each treatment group.

Sorting within tables ensures the same presentation for the set of all adverse events within the observation period (pretreatment and treatment-emergent). For that purpose, the table of all treatment-emergent adverse events presented by SOC and PT sorted by the internationally agreed SOC order and decreasing frequency of PTs within SOCs will define the presentation order for all other tables unless otherwise specified. Sorting will be based on results for the experimental treatment arm.

Analysis of all treatment-emergent adverse events

The following treatment-emergent adverse event summaries will be generated for the safety population.

- Overview of treatment-emergent adverse events, summarizing number (%) of patients with any
 - Treatment-emergent adverse event
 - Adverse event of special interest
 - Serious treatment-emergent adverse event
 - Treatment-emergent adverse event leading to death
 - Treatment-emergent adverse event leading to permanent study discontinuation
- All treatment-emergent adverse events by primary SOC and PT, showing the number (%) of patients with at least 1 treatment-emergent adverse event, sorted by the internationally agreed SOC order and by decreasing incidence of PTs within each SOC. This sorting order will be applied to all other tables, unless otherwise specified
- All treatment-emergent adverse events regardless of relationship and related by primary SOC, and PT, showing the number (%) of patients with at least 1 treatment-emergent adverse event, sorted by the internationally agreed SOC order. The PT level will be presented in alphabetical order
- All treatment-emergent adverse events by maximal severity, presented by primary SOC and PT, showing the number (%) of patients with at least 1 treatment-emergent adverse event by severity (ie, mild, moderate, or severe), sorted by the sorting order defined above

Analysis of all treatment emergent serious adverse event(s)

- All treatment-emergent serious adverse events by primary SOC, and PT, showing the number (%) of patients with at least 1 serious treatment-emergent adverse event, sorted by the internationally agreed SOC order. The PT level will be presented in alphabetical order
- All treatment-emergent serious adverse events regardless of relationship and related to IMP, by primary SOC, and PT, showing the number (%) of patients with at least 1 treatment-emergent serious adverse event, sorted by the internationally agreed SOC order. The PT levels will be presented in alphabetical order

Analysis of all treatment-emergent adverse event(s) leading to study discontinuation

- All treatment-emergent adverse events leading to study discontinuation, by primary SOC and PT, showing the number (%) of patients sorted by the internationally agreed SOC order. The PT level will be presented in alphabetical order
- PTs within each SMQ

Analysis of adverse event of special interest

- All adverse event of special interest by primary SOC and PT, showing the number (%) of patients sorted by the internationally agreed SOC order and decreasing incidence of PTs within each SOC

Analysis of pretreatment adverse events

- All pretreatment adverse events by primary SOC and PT, showing the number (%) of patients sorted by the internationally agreed SOC order and decreasing incidence of PTs within each SOC

2.4.5.2 Deaths

Any adverse events leading to death will be presented as a listing, indicating the study period (pretreatment or treatment-emergency period).

2.4.5.3 Analyses of laboratory variables

Not applicable.

2.4.5.4 Analyses of vital sign variables

The summary statistics (including number, mean, median, standard deviation, minimum and maximum) of all vital signs variables (central laboratory values and changes from baseline) will be calculated for each visit or study assessment (baseline, each post-baseline time point) by treatment group.

2.4.6 Analyses of quality of life

The analyses of quality of life has been described in [Section 2.4.4.4](#).

2.5 DATA HANDLING CONVENTIONS

2.5.1 General conventions

The following formulas will be used for computation of parameters.

Demographic formulas

Age in years = integer part of $((\text{date of informed consent} - \text{date of birth})/365.25)$

Vital signs formulas

BMI = weight in kilograms divided by height in meters squared

Prior or concomitant medications and therapeutic procedures derivation

Prior medications are those the patient used 26 weeks prior to first investigational medicinal product (IMP) injection. Prior medications can be discontinued before first administration or can be ongoing during treatment phase.

Concomitant medications are any treatments received by the patient concomitantly to the IMP, from randomization to the end of treatment.

A given medication can be classified both as a prior medication and as a concomitant medication.

2.5.2 Data handling conventions for secondary efficacy variables

For 7-day average WOMAC A1, the baseline value is defined as the average of the WOMAC A1 scores recorded 7 days prior to the first IMP administration (WOMAC A1 score recorded on Day 1 included). The 7-day average WOMAC A1 will be set as missing if 3 or more of the 7 WOMAC A1 scores were missing.

The analyses for change from baseline over 26 weeks for 7-day average WOMAC A1, WOMAC A, PTGA, and COGA are similar to the analyses for the primary effectiveness endpoint (SAP [Section 2.4.4.1](#)).

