	
 
Percentages of positive responders over 26 weeks, where response is defined as a <math>\geq 2</math>-point improvement from baseline in the WOMAC A1 NRS.
 
 
Safety will be assessed by evaluation of the incidence of treatment emergent adverse events (TEAEs) and changes in standard safety parameters (eg, vital signs) from screening visit through the last follow up visit.
 
Tertiary efficacy endpoints and other endpoint(s):
 
Tertiary efficacy endpoints include the differences between treatment groups in:
 
 
Changes from baseline at Week 4, 8, 12, 16, 20, and 26 in 7-day average walking pain score (measured by daily WOMAC A1)
 
Changes from baseline at Week 4, 8, 12, 16, 20, and 26 measured by WOMAC A1, WOMAC A, B, C and total, as well as PTGA and COGA
 
The amount and days of permitted pain rescue medication use at Week 4, 8, 12, 16, 20, and 26.
 
 
Quality of life variables include:
 
 
Changes of quality of life from baseline at Week 4, 8, 12, 16, 20, and 26 in EQ-5D scores.
 

ASSESSMENT SCHEDULE	
After providing informed consent, each patient will undergo screening visit assessments to determine study eligibility. Eligible patients will enter the wash-out period, during which time a patient will washout from prohibited pain and OA medications (ie, those with a half-life <math>> 5</math> hours, please refer to Appendix C). The wash-out period may last for up to 14 days, depending on the half-life of the medications. Following completion of the wash-out period, a patient will initiate baseline (Day-7 to Day-1) daily pain reporting using a patient diary. A patient's eligibility for participation in the study will be reevaluated at Day 1 to confirm that the patient continues to meet all study eligibility criteria. Study medication will be administered at Day 1. In case eligibility criteria are not met, the patient may be re-screened and will follow the same procedure as described in the flow chart from screening visit to Day 1. A new patient number will be allocated. Follow-up for efficacy and safety will be done at Week 1, 4, 8, 12, 16, 20, and 26.

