### 7.2 EXCLUSION CRITERIA

#### 7.2.1 Exclusion criteria related to study methodology

- E 01. Patient with painDETECT Questionnaire score  $>18$  at screening visit ([Appendix D](#))
- E 02. Patient with moderately severe or severe depression as indicated by PHQ-9 total score of  $\geq 15$  or a score of  $>0$  on item # 9 at screening visit ([Appendix D](#))
- E 03. Patient with severe anxiety as indicated by GAD-7 score of  $\geq 15$  at screening visit ([Appendix D](#))
- E 04. Patient does not record a minimum of 5 days' worth of diary data within the 7 days before the treatment day (Day 1)
- E 05. Patient with severe insomnia as indicated by ISI Questionnaire score  $>22$  at screening visit ([Appendix D](#))

---

 Anteroposterior view: weightbearing (extension or semi-flexion) + profile and a femoro-patellar view at 30° classical.

- E 06. Patient is not ambulatory (assistive device allowed if used 4 weeks or more prior to screening visit)
- E 07. The score of contralateral knee pain (if present) >3.0 NRS at screening visit
- E 08. Ipsilateral hip OA
- E 09. Patient with ALT/AST  $\geq 3 \times$  ULN and/or bilirubin  $\geq 1.5 \times$  ULN
- E 10. Female of childbearing potential who is unwilling to use effective contraceptive method throughout the duration of the study.
- E 11. Female who is pregnant or lactating
- E 12. Patient with active knee joint infections or skin diseases or infections in the area of the injection site of the target knee joint
- E 13. Patient with systemic corticosteroids within 12 weeks prior to screening visit
- E 14. Patient with injection of IA corticosteroids in the target knee joint within 26 weeks prior to screening visit
- E 15. Patient has visco-supplementation injection in any joint, including the target knee joint, within 26 weeks prior to screening visit
- E 16. Patient with concomitant inflammatory disease or other condition that affects the joints (eg, rheumatoid arthritis, metabolic bone disease, psoriatic arthritis, gouty arthritis, symptomatic chondrocalcinosis, osteonecrosis or active infection)
- E 17. Patient with secondary OA of the target knee joint due to acute disease or trauma within 5 years prior to screening visit
- E 18. Patient with significant valgus/varus deformities, ligamentous laxity, or meniscal instability

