### **9.2 SECONDARY ENDPOINTS**

#### **9.2.1 Secondary efficacy endpoint(s)**

Secondary efficacy endpoints include the differences between treatment groups in:

- Change from baseline over 26 weeks in 7-day average walking pain score (measured by daily WOMAC A1), WOMAC A, PTGA, and COGA
- Percentages of positive responders over 26 weeks, where response is defined as a  $\geq 2$ -point improvement from baseline in the WOMAC A1 NRS.

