### 11.4.2.2 Analyses of secondary efficacy endpoints

As with the primary effectiveness analysis, the secondary effectiveness analyses will be performed on the mITT population as well. For the analysis of the change from baseline in WOMAC A, PTGA, and COGA, repeated-measures ANCOVA will be used as described in the description of the primary effectiveness analysis.

For the analysis of WOMAC A1 responders ( $\geq 2$  point improvement on NRS Scale) generalized estimating equations (GEE) modeling will be used. Each responder (yes/no) endpoint evaluated at multiple post-baseline visits will be analyzed using GEE for binary outcomes. A GEE model will be fitted to the responder data and will include terms for baseline measure, site, visit, treatment group and a visit-by-treatment group interaction. Hypothesis testing will be performed using least squares means based on the linear predictor of the model.

For secondary efficacy analysis, the baseline is defined as the last available value prior to the injection of IMP after or on the randomization day, same as the primary efficacy analysis.

For the analysis of the percentages of positive responders, patients who discontinued the study prior to the Week 26 assessment due to either target knee-related AEs or due to lack of efficacy were classified as non-responders in the efficacy analysis. Patients who discontinued the study for other reasons had their responder status imputed using the LOCF method. The LOCF was used for all responder analyses, but not for the analysis of other parameters. No replacement on any missing or invalid data was made for the safety analyses.

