2.1.3 Efficacy endpoints

The baseline value for efficacy endpoints is defined as the last available value prior to the IMP administration or last available value on or before the date of randomization if not treated, unless otherwise specified.

WOMAC scores

The WOMAC NRS 3.1 questionnaire is a self-administered, health status measure used to probe symptoms of pain (WOMAC A), stiffness (WOMAC B), and function (WOMAC C) in patients with OA of the knee (1, 3). The questionnaire consists of 24 questions relating to the patient's assessment of his/her target joint pain (5 questions), stiffness (2 questions), and physical function (17 questions). An 11-point NRS ranging from 0 (None) to 10 (Extreme) will be used to capture the patient's response to each of the questions. All responses will be recorded directly on the paper patient questionnaire (PQ), and the PQ will serve as source documentation. The patient was asked to check the box that indicated his/her amount of target joint pain, amount of stiffness, and degree of difficulty completing tasks within the past 48 hours.

The WOMAC A consists of 5 questions assessing pain symptoms while walking, using stairs, at night while in bed, sitting or lying, and standing.

The WOMAC A1 is a single question within the WOMAC A that specifically assesses target knee pain while walking on a flat surface.

The WOMAC B consists of 2 questions assessing severity of stiffness that occurs after a period of inactivity later that same day.

The WOMAC C consists of 17 questions assessing physical function while performing the following activities: stair rise, rise from sitting, standing, bending, walking, getting in/out of a car, putting on/taking off socks, rising from bed, lying in bed, getting in/out of bath, sitting, getting on/off toilet, heavy household duties, and light household duties.

The WOMAC total score is computed as the sum of the available components of the 3 subscores: WOMAC A, WOMAC B and WOMAC C. The raw total WOMAC score ranges from 0 to 240, since the sums for the components of the 3 subscores range from 0 to 50 for the WOMAC A, 0 to 20 for the WOMAC B, and 0 to 170 for the WOMAC C. The total WOMAC score will be set to missing if any of the WOMAC subscores are set to missing as defined above. The raw total WOMAC score will be standardized to the 0 to 10 scale by dividing by 24.

Patient Global Self-Assessment (PTGA)

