2.1.3.2 Secondary efficacy endpoint(s)

Secondary efficacy endpoints include the differences between treatment groups in:

- Change from baseline over 26 weeks in 7-day average walking pain score (measured by daily WOMAC A1, 7-day average WOMAC A1), WOMAC A, B, C and total, as well as PTGA, and COGA
- Percentages of positive responders over 26 weeks, where response is defined as a ≥ 2 -point improvement from baseline in the WOMAC A1 NRS

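### SAP 2.5.2's baseline for the 7-day average WOMAC A1 cannot be seven scores, include Day 1 and keep the protocol's seven diary days all at once

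*SAP*

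**What the plan says.** **The endpoint.** Protocol 9.2.1 lists change from baseline in the "7-day average walking pain score (measured by daily WOMAC A1"; SAP 2.1.3.2 repeats it as "measured by daily WOMAC A1, 7-day average WOMAC A1". Both point to the daily diary.

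**The baseline rule.** SAP 2.5.2 defines the baseline as an "average of the WOMAC A1 scores recorded 7 days prior to the first IMP administration (WOMAC A1 score recorded on Day 1 included". Any such average is "set as missing if 3 or more of the 7 WOMAC A1 scores were missing".

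**The diary days.** In the protocol's Clinical Trial Summary, after wash-out "a patient will initiate baseline (Day-7 to Day-1) daily pain reporting using a patient diary". E 04 in protocol 7.2.1 excludes a patient with fewer than five days of diary data "within the 7 days before the treatment day (Day 1". Protocol Appendix E has the diary filled in once a day, preferably in the evening, with pain recorded only in the 7 days before each visit. Its Question 1 asks about walking pain over the last 24 hours.

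**The general baseline rules.** Protocol 11.4.2.2: "For secondary efficacy analysis, the baseline is defined as the last available value prior to the injection of IMP". SAP 2.1.3: "The baseline value for efficacy endpoints is defined as the last available value prior to the IMP administration", unless the SAP specifies otherwise.

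**The baseline period.** Protocol 6.2.1 and SAP 1.4 describe eight days including Day 1. The SAP 2.5.4 baseline window runs from Day -7 to Day 1.

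**The concern.** This baseline is subtracted from every follow-up 7-day average and is also the covariate in the model. If the text does not fix which days enter it, two programmers can derive different baselines from the same data.

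Two harms are possible. A patient who met E 04 could lose the baseline, and so leave the analysis, because Day 1 is counted and blank. SAP 2.4.4.2 limits LOCF to responder analyses and plans no sensitivity analyses for secondary endpoints, so such a patient would not be recovered. Alternatively, a diary score entered on the evening of Day 1, after the injection, could be averaged into the baseline. The two harms cannot occur in the same patient: the first needs the Day 1 score absent, the second needs it present.

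**Working it through.** **1. Counting the scores (there is no Day 0).** The SAP's own figure is seven.

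| Reading | Scores | Day 1 included | All protocol diary days kept |
|---|---|---|---|
| Day -7 to Day 1 | 7 + 1 = 8 | yes | yes |
| Day -6 to Day 1 | 6 + 1 = 7 | yes | no, Day -7 dropped |
| Day -7 to Day -1 | 7 | no | yes |

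The second and third readings reproduce the seven. Each reading fails one of the three conditions.

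**2. Missing rule against E 04.** Fewer than three missing of seven means at least five present, which is the E 04 threshold. The two rules coincide only if they are applied to the same seven days.

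Take E 04's diary data to mean pain scores. The completion patterns for Day -7 to Day -1 that pass E 04 number C(7,5) + C(7,6) + C(7,7) = 21 + 7 + 1 = 29.

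- Day 1 present: 0 of 29 lose the baseline, on either seven-score reading.
- Day 1 blank, Day -7 to Day -1: 0 of 29.
- Day 1 blank, Day -6 to Day 1: the losses are the five-entry patterns that include Day -7, because only four of the seven counted scores remain. That is C(6,4) = 15 of 29.

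These count patterns; they are not probabilities. For eight scores the SAP states no missing rule, so no count is given.

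**3. Expected loss on Day -6 to Day 1.** Assume that each day is completed independently with probability p. Given that E 04 is met and Day 1 is blank, the loss is 15p⁵(1 − p)² / P, where P is the probability of at least five of seven entries. If Day 1 is also completed with probability p, multiply by (1 − p).

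| p | P | Loss if Day 1 blank | Loss if Day 1 completed at rate p | Of 422 |
|---|---|---|---|---|
| 0.95 | 0.9962 | 0.0291 | 0.0291 × 0.05 = 0.0015 | 0.6 |
| 0.90 | 0.9743 | 0.0909 | 0.0909 × 0.10 = 0.0091 | 3.8 |

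If Day 1 were blank for every patient, the third column applies to all: 2.9% or 9.1%, about 12 or 38 of 422.

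**4. Source and timing of the Day 1 score.**

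- *Diary item:* 24-hour recall, preferably entered in the evening. Daily pain is recorded for the 7 days before each visit, and the protocol gives the pre-treatment diary as ending on Day -1. Day 1 then falls, if anywhere, in the diary week before the Week 1 visit. SAP 2.5.4 schedules that visit on Day 7 ± 4, so Day 3 to 11. Day 1 is within the preceding 7 days for visits on Day 3 to 8 and outside for Day 9 to 11. The score may therefore be absent or post-injection.
- *Site WOMAC A1:* 48-hour recall (protocol 10.1.7). Protocol 10.1.2 puts it among the assessments done before randomization and injection. It would be pre-injection and rarely missing, but would mix a 48-hour recall with 24-hour diary scores.

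SAP 2.5.2 does not say which is meant.

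**5. Size of any bias.** Let d be the between-arm difference in how far the injection shifts the Day 1 score, k the number of scores averaged, and beta the slope of follow-up on baseline. If every patient contributes a post-injection Day 1 score, the adjusted treatment difference moves by beta × d / k. With the assumed d = 1 and beta = 0.7, this is 0.7/7 = 0.10 points at k = 7 and 0.7/5 = 0.14 at k = 5, the fewest scores the rule allows. With d = 0.5, beta = 0.3 and k = 7 it is 0.02. If both arms shift equally it is zero.

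**The case against.** The strongest reply is that SAP 2.5.2 agrees with itself. It says that Day 1 is included and then refers to seven scores, so the natural reading is Day -6 to Day 1. E 04 is an eligibility rule, and nothing obliges the analysis baseline to use the same days. The eight-day baseline period and the SAP 2.5.4 window both contain Day 1. The Day 1 score may be the site questionnaire, completed before the injection, in which case neither harm arises. And the documents repeatedly ask for a pre-injection value.

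Much of this stands. A reader might infer that the SAP contradicts its own count; it does not, because Day -6 to Day 1 is seven scores. A reader might also infer that dozens of patients would be lost; that needs Day 1 to be blank for nearly everyone, which no section says. Nor do the documents show that the baseline is contaminated: SAP 2.5.2, SAP 2.1.3 and protocol 11.4.2.2 all call for values before the injection, so a post-injection entry is possible, not expected.

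What the reply does not settle is which days and which instrument apply. The Day -6 to Day 1 reading discards a diary day that the protocol collects for this purpose. The site-score reading sits poorly with an endpoint defined by the daily score. An eight-day baseline period does not make eight diary days.

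**Conclusion.** Wrong as written, and minor. The SAP's count of seven, its inclusion of Day 1 and the protocol's seven pre-treatment diary days cannot all hold, and the source of the Day 1 score is not stated.

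That much rests on the text alone. The sizes rest on assumptions: independent daily completion at 95% or 90%, Day 1 completed like any other day, and the values of d and beta. Under these the loss on Day -6 to Day 1 is under 1 or about 4 of 422 patients. It is zero when a Day 1 score is present, and larger losses need Day 1 to be blank for most patients. Any bias needs an unequal shift between arms and is about 0.10 to 0.14 points at the larger assumed inputs.

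The effect is confined to one of the five secondary endpoints in the Hochberg family and its exploratory by-visit versions. The primary endpoint uses its own baseline and is unaffected.

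**What to change.** In SAP 2.5.2, define this baseline as the mean of the diary Question 1 pain scores dated Day -7 to Day -1, with at least five of the seven present and Day 1 excluded. State that this is the specified exception to the general baseline rule in SAP 2.1.3. The definition then matches the protocol's diary days, E 04 and the SAP's own missing rule, and every score precedes the treatment day.

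A lighter alternative is to keep Day 1, list the seven study days and name the source and timing of the Day 1 score. That removes the ambiguity but leaves the mismatch with E 04.

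The cost is SAP wording only, since the data are already collected. A valid pre-injection Day 1 score, where one exists, would go unused. One gap remains: E 04 counts diary data, and the diary also has a rescue-medication question, so a patient who met E 04 on rescue entries without pain scores could still lack a baseline.
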